#### The following contrasts will be explored (total IgG and IgG subclasses 1-4):

Q3W schedule - Css/D for 7th infusion vs baseline

Q4W schedule - Css/D for 5th infusion vs baseline

The formula for calculation of the estimated ratio between the test and reference and the  $(1-2^{*}\alpha)^{*}100$  % CI of the ratio is given below.

Difference = Estimate of difference between test and reference least square means  $Ratio = 100 \times e^{Difference}$   $(1-2^{*}\alpha)^{*}100\%$  Cls for the Ratio:  $Lower = 100 \times e^{(LowerBound (1-2^{*}\alpha)\%Cls for the Difference)}$  $Upper = 100 \times e^{(UpperBound (1-2^{*}\alpha)\%Cls for the Difference)}$ 

Comparison between BT595 and previous IVIG products will also be explored graphically with box plots of  $C_{ss}/D$  as described in Section 9.6.5Fehler! Verweisquelle konnte nicht gefunden werden. of the SAP.

#### 9.8. EXPLORATORY COMPARISON OF STEADY-STATE PK PARAMETERS FOR TOTAL IGG, IGG SUBCLASSES AND SPECIFIC IGGS BETWEEN AGE CATEGORIES

Exploratory comparison of  $CL_{ss}$ , not dose-normalized and dose-normalized,  $C_{max}/D$ ,  $AUC_{tau}/D$  and if available  $AUC_{0-inf}/D$  using Dense PK Subset and  $C_{ss}$  and  $C_{ss}/D$  separately using the PK Trough set and the Specific IgG Trough PK set for the Q3W schedule and the 5th infusion for the Q4W schedule between age categories will be performed for total IgG, IgG subclasses and antigen specific IgGs by ANOVA approach as described above. Only subgroups with at least n=3 subjects will be retained for the comparison test.

Dense PK Subset will be used for the comparison of PK parameters. The PK Trough set and Specific IgG Trough PK set will be used for comparison of trough concentrations at steady state.

Log-transformed parameters for total IgG, IgG subclasses and specific IgGs will be compared separately by infusion schedule between age categories.

The same model will be repeated for dose normalized trough concentration and CLss.

The following contrasts will be explored:

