# 3.7. ADMINISTRATION OF STUDY MEDICATION

The planned dose of BT595 is 0.2 to 0.8 g/kg body weight (2 to 8 mL/kg) administered as intravenous infusions at 3- or 4-week intervals for a treatment period of approximately 12 months.

**Infusion rate:** BT595 is infused intravenously at an initial rate of 0.3 mL/kg/h for 30 minutes, and increased to 1.4 mL/kg/h for a further 30 minutes. If well tolerated, the rate of administration is then gradually increased to a maximum of 2.0 mL/kg/h for the remainder of the first infusion. From the second infusion, in subjects who have tolerated the infusion rate of 2.0 mL/kg/h well, the rate may be gradually increased to 4 mL/kg/h, and if still tolerated well, it may be further increased gradually to 6 mL/kg/h, and to a maximum of 8 mL/kg/h.

From the second infusion, subjects' infusion rates may be individually tailored (i.e., a certain infusion rate for a certain time period) at the discretion of the investigator, but must start again at an initial infusion rate of 0.3 mL/kg/h. This means that the 30 minute interval could be shortened to less than 30 minutes if deemed appropriate for the subject. Changes in infusion rates (increases and/or decreases) and the respective time of day are to be documented.

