#### 9.4.3. Steady State Trough Concentrations (Multiple PK Sets)

For comparison purpose, steady state trough concentrations ( $C_{ss}$ ), defined as the trough concentration prior to infusion 7 for Q3W schedule and infusion 5 for Q4W, and measured both at local lab and at central lab (Biotest), will be listed for each subject. The steady state trough concentrations will be summarized separately for PK Trough set (local lab) for all subjects and for the Dense PK Subset (central lab) only for subjects participating to steady state PK study combined by age and dosing regimen (Q3W or Q4W). The comparison between local lab and central lab measurements will be done graphically for the subjects in Dense PK Subset as described in Section 9.6.3.

Antigen-specific IgGs will be summarized in a separate table for Specific IgG Trough PK Set.

In addition, steady-state trough concentrations Css of total IgG normalized by dose level i.e. divided by actual administered dose will also be calculated. Latest dose level before measurement will be used for dose normalization.

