AUC 0-t /D	AUC 0-t normalized by dose level
AUC tau	Area under the serum concentration-time curve from time of dosing (infusion 7(Q3W) or 5 (Q4W)) to the end of dosing interval
AUC tau /D	AUCtau normalized by dose level
MRT	Mean residence time
Cavg	Average serum concentration over the dosing interval following infusion 7 (Q3W) or 5 (Q4W) calculated by dividing AUC tau over dosing interval (tau)
Css	Steady-state trough concentrations measured prior to infusion 7 (Q3W)/ 5 (Q4W) dosing interval
C ss /D	Steady-state trough concentrations measured prior to infusion 7 (Q3W)/ 5 (Q4W) dosing interval normalized by dose level
% Fluctuation	% fluctuation is computed as $100^{(C_{max}-C_{min})/C_{avg}}$ , where Cmin and C max measured over dosing interval following infusion 7 (Q3W)/ 5 (Q4W) dosing interval
CLss	An estimate of the total body clearance = Dose/AUCtau
Vss	Volume of distribution at steady-state
AUC 0-inf	Area under the concentration-time curve from time of dosing (infusion 7(Q3W)/ 5 (Q4W) extrapolated to infinity
AUC 0-inf /D	AUC 0-inf normalized by dose level
t 1/2	Serum terminal elimination half-life (time to reduce concentration by half during the terminal phase of the profile)
λz	terminal elimination rate constant

Clast	Last measured quantifiable concentration
tlast	Time point for the last measured quantifiable concentration

The noncompartmental analysis will be performed using an appropriate software solution. For the derivation of the PK parameters, the sampling time of pre-dose samples relative to dosing will be treated as time zero, using days as time units.

The PK parameters will be estimated as follows:

- The apparent Cmax and the corresponding tmax will be read directly from the concentrationtime plot of the observed data (not predicted data by the software);
- AUCs will be calculated using the linear/log trapezoidal rule.
- The terminal elimination rate constant ( $\lambda_z$ ) will be generally determined by log-linear regression obtained using the 3 last quantifiable concentrations and will not include Cmax. The adjusted square of the correlation coefficient (Rsquare adjusted) for the goodness of fit of the regression line through the data points must be at least 0.8500 for the  $\lambda_z$  value to be considered adequately reliable.

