#### Statistical Analysis Plan

#### Version Final 2.0

Cmax to calculate  $\lambda_z < 3$ ),  $\lambda_z$ ,  $t_{1/2}$ , AUCinf will be flagged based on the specific criteria in the individual data listings.

- CLss is calculated by program as (Dose/AUCtau).
- For subjects with unreliable AUCinf (because of extrapolation >25%), AUCinf will be reported, but flagged in the individual data.

All PK parameters will be estimated both by baseline corrected and baseline uncorrected.

Flagged PK parameters will only be included in summarization and statistical analyses after careful consideration.

The PK parameters derivation will be based on data availability for analytes total IgG, or total IgG and IgG subclasses, and antigen-specific IgG by different age categories. Data for different analytes will be summarized in separate tables.

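### SAP 9.8 adds a dose-normalised CLss to the age comparison; CLss already contains the dose, so this variant is 1/AUCtau and not a clearance

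*SAP*

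**What the plan says.** SAP 9.8 sets out ANOVA comparisons of log-transformed PK parameters between age categories, separately by infusion schedule. Its opening sentence lists CLss as "not dose-normalized and dose-normalized", next to Cmax/D, AUCtau/D, AUC0-inf/D if available, Css and Css/D. Its closing sentence before the contrasts is "The same model will be repeated for dose normalized trough concentration and CLss".

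SAP 9.5.1 defines CLss as "An estimate of the total body clearance = Dose/AUCtau", and the calculation rules later in that section repeat the same formula. The meaning of the /D suffix is also set there: AUCtau/D, for example, is "AUCtau normalized by dose level". For the total IgG trough, SAP 9.4.3 describes the quantity as "normalized by dose level i.e. divided by actual administered dose will also be calculated", without a unit.

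No CLss/D appears in the derived-parameter list of 9.5.1 or in the summary table of 9.5.2. On dose, SAP 3.7 says "The planned dose of BT595 is 0.2 to 0.8 g/kg body weight (2 to 8 mL/kg"; SAP 3.6 has each subject start on a dose consistent with prestudy treatment.

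**The concern.** Dose normalisation suits quantities that rise with dose, such as AUC, Cmax and trough, because it removes the dose before groups are compared. Clearance has already had this done to it, since dose is its numerator. Dividing again does not adjust for dose. It takes out the adjustment that makes clearance comparable between subjects on different doses.

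The result would still carry the label of a clearance. A reader of the age tables could see two CLss results, one with and one without dose normalisation, that disagree. Such a reader might reasonably, but wrongly, trust the normalised one more. The risk runs both ways: a difference in prescribed dose can appear as a difference in clearance, and a difference in clearance can be cancelled by a difference in dose.

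**Working it through.** The plan gives no figure of its own to reproduce here. The check is algebra, followed by illustrations.

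**Inputs from the documents.** CLss = Dose/AUCtau (SAP 9.5.1). The /D suffix means division by dose level (SAP 9.5.1). Planned doses are 0.2 to 0.8 g/kg (SAP 3.7), individual and carried over from prestudy treatment (SAP 3.6). Analysis is on the log scale (SAP 9.8).

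**Assumed inputs.** The documents give no mean doses by age category. The dose pairs below are assumptions within the planned range.

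**Step 1, algebra.** With the same dose D in both places:

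- CLss/D = (D/AUCtau)/D = 1/AUCtau
- log(CLss) = −log(AUCtau/D)
- log(CLss/D) = −log(AUCtau)

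Plain CLss and AUCtau/D therefore carry the same information with opposite sign. Dose-normalised CLss carries the information in unadjusted AUCtau.

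**Step 2, equal true clearance.** Let both groups have clearance CL, so AUCtau = D/CL. The group 1 to group 2 ratio of CLss/D is (1/D1)/(1/D2) = D2/D1.

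| Mean dose, group 1 vs group 2 (g/kg) | CLss ratio | AUCtau/D ratio | CLss/D ratio |
|---|---|---|---|
| 0.4 vs 0.4 | 1.00 | 1.00 | 0.4/0.4 = 1.00 |
| 0.4 vs 0.5 | 1.00 | 1.00 | 0.5/0.4 = 1.25 |
| 0.4 vs 0.6 | 1.00 | 1.00 | 0.6/0.4 = 1.50 |
| 0.3 vs 0.6 | 1.00 | 1.00 | 0.6/0.3 = 2.00 |
| 0.2 vs 0.8 (limits of the range) | 1.00 | 1.00 | 0.8/0.2 = 4.00 |

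The lower-dosed group appears to clear faster. For scale, the ANOVA approach of SAP 9.7, to which 9.8 refers back, uses limits of 80% to 125%. The 0.4 vs 0.5 pair already puts the point estimate at the upper limit.

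**Step 3, a real difference hidden.** Suppose group 1 has 1.5 times the clearance of group 2 and is dosed at 0.6 against 0.4 g/kg. The CLss ratio is 1.50. The CLss/D ratio is 1.50 × (0.4/0.6) = 1.00. This is not far-fetched: under SAP 3.7.1 the dose is adjusted when the trough falls below 5 g/L, which can tie dose to clearance.

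**Step 4, how often it would mislead.** A simulation of the log-scale two-group comparison assumed equal clearance, 10 vs 20 subjects, a CV of 30% for clearance and 20% for dose, and a two-sided 10% level to match a 90% confidence interval (4,000 runs). A difference was declared in:

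| Typical dose, group 1 vs group 2 (g/kg) | CLss | CLss/D |
|---|---|---|
| 0.5 vs 0.5 | 8.5% | 8.9% |
| 0.45 vs 0.55 | 11.0% | 41.0% |
| 0.4 vs 0.6 | 9.5% | 88.5% |

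**Step 5, mixed units.** If CLss were computed from total grams and D were in g/kg, then CLss/D = body weight/AUCtau. That still carries dose differences and now adds body weight, so it is not a clearance either.

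**The case against.** The closing sentence of 9.8 is ambiguous by itself, because dose normalisation could attach to the trough only. As no CLss/D is derived in 9.5.1 or summarised in 9.5.2, a drafting slip is plausible. However, the opening sentence asks for both forms of CLss and lists Css and Css/D separately. No other section gives dose-normalised CLss a different meaning. Slip or not, the text needs correcting.

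The strongest objection concerns consequence, and it stands. Plain CLss and AUCtau/D are both compared in 9.8, so the valid clearance comparison is effectively planned twice. The section is headed exploratory, and Protocol 10.10 foresees only descriptive comparison of age categories. The effects of age and weight on paediatric PK, with allometric scaling, are also to be examined in the population PK analysis of SAP 9.10, if that goes ahead. No decision rule depends on CLss/D.

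Three stronger readings are tempting, and the documents support none of them:

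- **That clearance is replaced by inverse exposure.** It is not; one invalid variant is added beside valid ones.
- **That D is in grams, so every /D parameter mainly reflects body weight.** Although 9.4.3 gives no unit for the administered dose, SAP 9.4.1, 9.4.4 and 9.5.2 use dose levels in g/kg bins. The sentence after the quoted one in 9.4.3 returns to dose level. Actual g/kg is the natural reading.
- **That small children would be set against adults with a several-fold weight distortion.** No planned contrast in 9.8 pairs children under 12 with adults. The 2 to <6 group is compared only with the 6 to <12 group, and only on Css and Css/D.

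**Conclusion.** The point holds as a limited error of analysis choice. On the SAP's own definition, dose-normalised CLss equals 1/AUCtau when the same dose is used twice, and it is not a clearance under the mixed-unit reading either. With equal clearance, its ratio between age groups is simply the inverse ratio of their doses: 1.25 to 1.50 for the moderate dose gaps assumed, and 4.00 at the limits of the planned range. The identity needs no assumption beyond the common dose unit. The sizes do rest on assumptions, because mean doses by age are not given; if doses proved equal across ages, no distortion would arise. The simulation rates depend further on the assumed group sizes and variability. The harm is a misleading exploratory result, with no effect on the primary endpoint or on the valid PK comparisons. The missing unit for D in 9.4.3 is a matter of clarification.

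**What to change.** In SAP 9.8, delete dose-normalised CLss from both the opening sentence and the sentence that repeats the model. Keep plain CLss and state that it is expressed per kg, that is, dose in g/kg divided by AUCtau. If a comparison of unadjusted exposure is wanted, plan it as AUCtau and label it so.

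As a clarification, add one line in 9.4.3 or 9.5.1 that D in every /D parameter is the actual dose in g/kg.

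The cost is two short deletions, one definition and the removal of the corresponding outputs. No data collection changes. No clearance information is lost, because log CLss is the negative of log AUCtau/D and both are already compared.

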#### Total IgG:

Regulatory agency	Age category 1 for comparison*	Age category 2 for comparison*		
FDA	2 to <6**	6 to <12		
	6 to <12	12 to <17		
	12 to <17	17 to <76		
	12 to <17	17 to <65		
	17 to <65	>=65		
EMA	2 to <6**	6 to <12		
	6 to <12	12 to <18		
	12 to <18	18 to <76		
	12 to <18	18 to <65		
	18 to <65	>=65		

\* if data from at least n=3 subjects available

\*\* comparison with 2 to <6 years old category will be done only for  $C_{ss}$  and  $C_{ss}/D$  parameters due to differences in PK sampling schedule with other age categories

#### IgG subclasses (each subclass individually):

Regulatory agency	Age category 1 for comparison	Age category 2 for comparison
FDA	6 to <12	12 to <17
	12 to <17	17 to <76
	12 to <17	17 to <65
	17 to <65	>=65
EMA	6 to <12	12 to <18
	12 to <18	18 to <76
	12 to <18	18 to <65
	18 to <65	>=65

#### Specific IgGs:

Regulatory agency	Age category 1 for comparison	Age category 2 for comparison
FDA	12 to <17	17 to <76
	12 to <17	17 to <65
	17 to <65	>=65
EMA	12 to <18	18 to <76
	12 to <18	18 to <65
	18 to <65	>=65

#### 9.9. EXPLORATORY COMPARISONS BETWEEN PK PARAMETERS DERIVED FROM COMPLETE AND REDUCED DATASETS

## 9.9.1. Exploratory Comparisons between Continuous PK Parameters Derived from Complete and Reduced Datasets

PK parameters derived from complete and reduced datasets for total IgG as described in Section 9.5.1 will be compared using the ANOVA approach described in Section 9.7.

The endpoints for comparison will be  $C_{max}$ , AUCtau, AUCinf,  $C_{max}/D$ , AUCtau/D, AUC0-inf/D derived from both complete and reduced datasets.

The following contrasts will be explored Full dataset vs reduced set 1 Full dataset vs reduced set 2 Full dataset vs reduced set 3 Full dataset vs reduced set 4 Reduced set 2 vs reduced set 1 Reduced set 3 vs reduced set 1 Reduced set 4 vs reduced set 1 Reduced set 3 vs reduced set 2 Reduced set 4 vs reduced set 2 Reduced set 4 vs reduced set 2 Reduced set 4 vs reduced set 2

# 9.9.2. Exploratory Comparisons between Tmax Derived from Complete and Reduced Datasets

Tmax parameter derived from complete and reduced datasets for total IgG as described in Section 9.5.1 will be compared using the Friedman approach.

 $T_{max}$  comparisons between reduced and full PK sets for total IgG using Dense PK Subset for ages 6 to <76 years old will be analyzed using Friedman's test. Pairwise treatment comparisons will be assessed using the Wilcoxon sign-rank test on the within-subject differences. The model will include only type of the sets.

The following contrasts will explored

Full dataset vs reduced set 1 Full dataset vs reduced set 2 Full dataset vs reduced set 3 Full dataset vs reduced set 4 Reduced set 2 vs reduced set 1 Reduced set 3 vs reduced set 1 Reduced set 4 vs reduced set 1 Reduced set 3 vs reduced set 2 Reduced set 4 vs reduced set 2 Reduced set 4 vs reduced set 3

#### 9.10. **POPULATION PK ANALYSIS**

Population PK analysis is planned to obtain further information for the sparse PK sampling data from subjects in the age category 2 to <6 years. The decision to proceed with population PK analysis will be made as soon as all PK data are collected; results of the exploration using "in silico" reduced data set (Section 9.9) may also be taken into consideration. if available.

The population PK analysis will be performed according to the regulations from FDA and EMA for population PK analysis [Food and Drug Administration (FDA) Guidance for Industry: Population Pharmacokinetics. February 1999. Available from http://www.fda.gov/downloads/Drugs/GuidanceComplianceRegulatoryInformation/Guidanc es/ucm072137.pdf, European Medicines Agency Guideline On Reporting The Results Of Pharmacokinetic Population analyses. June 2007. Available from: http://www.ema.europa.eu/docs/en GB/document library/Scientific guideline/2009/09/W C500003067.pdf].

The population PK model will be developed using dense PK sampling, for all available subjects in the study from age categories 6 to <76 years as well as the sparse sampling from the 2 to <6 years pediatrics subjects.

Covariates of interest will be evaluated for their effect on pediatric PK (e.g. age, and weight). Allometric scaling of the centered covariates (weight) will be tested.

The best population PK model will be evaluated using visual predictive checks and bootstrap approach.

The details of the population PK analysis as well as the acceptance criteria for the visual predicted check (VPC), terms of model evaluation and guality procedures for population PK output will be further described in a separate population PK analysis plan.

## **10.** ANALYSIS OF PHARMACODYNAMICS

Pharmacodynamic analysis is described as efficacy analysis based on the secondary efficacy endpoint of trough concentrations of total IgG as described in Section 8.2.1 of the SAP.

Additionally to the analyses described above the changes in dosing levels due to values of secondary endpoints of total IgG trough concentrations below the target levels will be summarized based on the starting dose level for each subject.

Frequency of dose adjustments by treatment schedule, age category, starting dose, time of adjustment (infusion number) and overall will be presented in summary table.

## 11. SAFETY

All analyses described in this section will be performed using the SAF and will be presented by treatment schedule (3- or 4 week) and overall, if not stated otherwise. The results will be descriptive in nature. All data will be summarized and listed.

In addition, all safety parameters will be presented stratified by age categories, gender, race and region as defined in Section 6.6. Age classes will be presented separately by FDA and by EMA criteria. The pediatric population (young children, children and adolescents) will be presented as a subtotal.

Safety will be assessed on the basis of AEs, laboratory parameters (routine safety and intravascular hemolysis), vital signs, and physical examination.

### 11.1. EXTENT OF EXPOSURE

The duration of exposure will be expressed as the time in days from the first infusion of BT595 through to the last visit (inclusive). Summaries will be for a continuous variable and also by categorizing the data according to the following categories:

 $\leq$  1 month >1 -  $\leq$  2 months >2 -  $\leq$  3 months etc.

The total number of administered infusions will be summaries for a continuous variable and by categorizing the data according to the following categories:

 $1 - \le 2$  infusions  $3 - \le 4$  infusions  $5 - \le 7$  infusions  $8 - \le 11$  infusions >11 infusions

The actual calculated dose in g/kg, based on the total dose administered and body weight at a given visit, will also be calculated at each infusion.

The following will be summarized:

- The actual dose in g/kg,
- The actual dose in g and ml for each infusion
- Number of subjects with dose modification or dose interruption for each infusion together with the reason for changes in the dose.
- Changes of planned infusion rate [ml/kg/h] during any infusion and the reason for change.
- Maximal administered infusion rate [ml/kg/h] in categories: ≤0.3, >0.3 ≤1.4; >1.4 ≤2; >2 ≤4; >4 ≤6; >6

- The total dose administered in g and ml across all infusions.
- Duration of infusion in min for each infusion.

Additionally, extent of exposure will be presented for PK Trough Set and age categories defined in the Section 6.6.

#### 11.2. TREATMENT COMPLIANCE

BT595 is administered intravenously by the instructed study staff. If a subject's treatment deviates from the dosage regimen (e.g., a dosing interruption occurs due to the occurrence of an AE), this will be recorded in the eCRF.

If a subject fails to comply with the dosage regimen (i.e., misses  $\geq 1$  dose[s] of BT595), the subject will be considered to be noncompliant and may be terminated prematurely from the study. The decision to terminate a subject from the study prematurely will be at the investigator's discretion after consultation with the sponsor. Details of any deviations from the dosage regimen will be recorded in the eCRF.

### 11.3. ADVERSE EVENTS

Adverse events (AEs) will be coded using MedDRA, version 19.0, to give a preferred term and a SOC term for each event. At the end of the study, prior to database closure, AEs will be recoded applying the latest available MedDRA version available at this time point.

Adverse events temporally associated with the infusion are AEs occurring during infusion or within 1, 24, and 72 hours after the end of infusion and are defined as infusional AEs.

Summary tables will be based on treatment-emergent adverse events (TEAEs), defined as those events with onset date/time at or after the first BT595 infusion until the subject's last study visit. All tables will be displayed for overall AEs and for each treatment schedule.

**Thromboembolic events** ([TEEs], such as stroke, myocardial infarction, lung embolism) and **hemolysis** are defined as adverse events of special interest (AESIs) in this study.

The above mentioned AESIs will be retrieved from the database by the investigator assessment and by use of the following MedDRA Standard Queries (SMQ), separately:

-TEEs:	(1) MedDRA SMQ Embolic and thrombotic events
	(2) MedDRA SMQ Thrombophlebitis

-Hemolysis MedDRA SMQ Haemolytic disorders

Adverse drug reactions (ADR) of an IMP are all untoward and unintended responses to an IMP related to any dose administered.

All AEs judged by either the reporting investigator or the sponsor as having a reasonable causal relationship to a medicinal product qualify as ADRs (= related AEs).

Tables will be presented overall and stratified by age categories defined in the Section 6.6., as listed below:

An overall summary of AEs will show the number and percentage of subjects (and the corresponding number of AEs) who report

- any AEs,
- any TEAEs (overall, infusional and noninfusional),
- any related TEAEs (overall, infusional and noninfusional),
- any TEAEs by maximum severity (overall, infusional and noninfusional),
- any serious TEAEs (overall, infusional and noninfusional),
- any nonserious TEAEs (overall, infusional and noninfusional),
- any serious related TEAEs (overall, infusional and noninfusional),
- any nonserious related TEAEs (overall, infusional and noninfusional),
- any TEAEs leading to study drug infusion interruption,
- any TEAEs leading to study drug dose reduction
- any TEAEs leading to study discontinuation / withdrawal,
- any TEAEs of special interest (investigator assessment / SMQ information, separately for TEE and Hemolysis),
- any TEAEs not caused by infection or infestation (defined by SOC),
- any TEAEs leading to death

The exploratory 2-sided 90% exact confidence limit interval will be calculated for the total number of subjects with TEAEs expressed as a percentage and the corresponding number of noninfusional TEAEs and corresponding to this for the infusional TEAEs.

The incidence of AEs and TEAEs (number and percentage of subjects reporting an event, and the number of events) will be summarized by SOC and preferred term.

Treatment emergent adverse events will be listed separately for two categories: with and without infections. In addition, the infections will be listed separately within the efficacy section. Additionally, summary by SOC and preferred term will be provided for infections.

The number and percentage of subjects with related TEAEs, and the number of related TEAEs will be summarized by SOC and preferred term.

If counted per subject and if more than 1 related TEAE is recorded for a subject within any SOC or preferred term, the subject will be counted only once.

The number and percentage of subjects with TEAEs and the number of preferred terms per MedDRA SOC will be summarized by maximum severity. If counted per subject and if more than 1 TEAE is recorded for a subject within any SOC or preferred term, the subject will be counted only once at the worst severity.

The number and percentage of subjects with noninfusional TEAEs and the number of preferred terms per MedDRA SOC will be summarized by maximum severity. If counted per

subject and if more than 1 TEAE is recorded for a subject within any SOC or preferred term, the subject will be counted only once at the worst severity.

The number and percentage of subjects with serious TEAEs and related serious TEAEs will be summarized by SOC and preferred term.

The number and percentage of subjects with TEAEs of special interest (separated by investigator assessment and SMQ information) and ADRs will be summarized by SOC and preferred term.

